8.2 SAFETY AND OTHER ASSESSMENTS

The CDS tool uses patient information in the electronic medical records to apply evidence-based algorithms that identify eligible patients, compute cardiovascular risks, prioritize cardiovascular risk factors, alert to potential medication issues, provide treatment recommendations, and promote adherence assessments and action plans. The study team has extensive experience in health services research and clinical research with human subjects, with procedures to safeguard privacy and personal information. See section 10.1.3 below on a detailed description of procedures put in place to assess and ensure safety of patient information.

8.3 ADVERSE EVENTS AND SERIOUS ADVERSE EVENTS

8.3.1 DEFINITION OF ADVERSE EVENTS (AE)

AE means any untoward medical occurrence associated with the use of an intervention in humans, whether or not considered intervention-related^{107,108}.

8.3.2 DEFINITION OF SERIOUS ADVERSE EVENTS (SAE)

An AE or suspected adverse reaction is considered "serious" if, in the view of either the investigator or sponsor, it results in any of the following outcomes: death, a life-threatening adverse event, inpatient hospitalization or prolongation of existing hospitalization, a persistent or significant incapacity or substantial disruption of the ability to conduct normal life functions, or a congenital anomaly/birth defect. Important medical events that may not result in death, be life-threatening, or require hospitalization may be considered serious when, based upon appropriate medical judgment, they may jeopardize the participant and may require medical or surgical intervention to prevent one of the outcomes listed in this definition. Examples of such medical events include severe hypoglycemia requiring intensive treatment in an emergency room or at home, elevated blood pressure or convulsions that do not result in inpatient hospitalization.

8.3.3 CLASSIFICATION OF AN ADVERSE EVENT

8.3.3.1 SEVERITY OF EVENT

For AEs not included in the protocol defined grading system, the following guidelines will be used to describe severity.

- **Mild** Events require minimal or no treatment and do not interfere with the participant's daily activities.
- Moderate Events result in a low level of inconvenience or concern with the therapeutic measures. Moderate events may cause some interference with functioning.
- Severe Events interrupt a participant's usual daily activity and may require systemic drug therapy or other treatment. Severe events are usually potentially life-threatening or incapacitating. Of note, the term "severe" does not necessarily equate to "serious".

8.3.3.2 RELATIONSHIP TO STUDY INTERVENTION

All AEs must have their relationship to study intervention assessed by the clinician who examines and evaluates the participant based on temporal relationship and his/her clinical judgment. The degree of certainty about causality will be graded using the categories below.

- **Related** The AE is known to occur with the study intervention, there is a reasonable possibility that the study intervention caused the AE, or there is a temporal relationship between the study intervention and event. Reasonable possibility means that there is evidence to suggest a causal relationship between the study intervention and the AE.
- Not Related There is not a reasonable possibility that the administration of the study intervention caused the event, there is no temporal relationship between the study intervention and event onset, or an alternate etiology has been established.

An AE will be considered unexpected if the nature, severity, or frequency of the event is not consistent with the risk information previously described for the study intervention.

8.3.4 TIME PERIOD AND FREQUENCY FOR EVENT ASSESSMENT AND FOLLOW-UP

With DSMB approval, this study will implement a passive surveillance strategy for potential AE's related to the study intervention. Data will be analyzed using model-predicted percentages of patients with safety conditions of interest for defined time periods during the intervention. Logistic regression models are used to generate predicted proportions by randomized treatment group controlling for age and baseline characteristics.

The occurrence of an AE or serious adverse event (SAE) may also come to the attention of project team members during patient and provider survey results and interviews with stake holders. These AEs not meeting the criteria for SAEs will be captured on the appropriate report forms. Information to be collected includes event description, time of onset, clinician's assessment of severity, relationship to study product (assessed only by those with the training and authority to make a diagnosis), and time of resolution/stabilization of the event. All AEs occurring while on study will be documented appropriately regardless of relationship. All AEs will be followed to adequate resolution.

Changes in the severity of an AE will be documented to allow an assessment of the duration of the event at each level of severity to be performed. AEs characterized as intermittent require documentation of onset and duration of each episode.

The project manager, in collaboration with the PI will record all reportable events with start dates occurring any time after inclusion into the study population until 7 (for non-serious AEs) or 30 days (for SAEs) after the last day of study participation. At each clinic visit, the project team member(s) will inquire about the occurrence of AE/SAEs since the last visit. Events will be followed for outcome information until resolution or stabilization.

8.3.5 ADVERSE EVENT REPORTING

According to the HealthPartners Institute IRB policies, investigators must report the specified adverse events or issues to the IRB as soon as possible, but in no event later than 10 working days after the investigator first learns of the event. Investigators or the project team must report possible problems or issues with the research to the IRB Office in writing using the Unanticipated Problem/Serious Adverse Event Form. The written report should contain the following: Detailed information about the event or issue, including relevant dates; Any corrective and preventative actions, planned or already taken, to ensure that the issue or problem is corrected and will not occur again; An assessment of whether any subjects or others were placed at risk as a result of the event or suffered any harm (e.g., physical, social, financial, legal or psychological) and any plan to address these consequences.

8.3.6 SERIOUS ADVERSE EVENT REPORTING

The study investigator shall complete an Unanticipated Adverse Device Effect Form and submit to the study sponsor and to the reviewing Institutional Review Board (IRB) as soon as possible, but in no event later than 10 working days after the investigator first learns of the effect.

Participating clinics will be informed of AEs and SAEs through communication with the clinic and healthcare group leadership and providers. Although unlikely, if specific patients are affected or at risk, they will be contacted through their routine patient communication channels and through their providers.

8.3.8 EVENTS OF SPECIAL INTEREST Not-Applicable

8.3.9 REPORTING OF PREGNANCY

Pregnancy is an exclusion criteria for the study. However, reporting is not warranted as there is no direct harm anticipated from the study.

8.4 UNANTICIPATED PROBLEMS

8.4.1 DEFINITION OF UNANTICIPATED PROBLEMS (UP)

The Office for Human Research Protections (OHRP) considers unanticipated problems involving risks to participants or others to include, in general, any incident, experience, or outcome that meets ALL of the following criteria:

- Unexpected in terms of nature, severity, or frequency given (a) the research procedures that are described in the protocol-related documents, such as the Institutional Review Board (IRB)approved research protocol and informed consent document; and (b) the characteristics of the participant population being studied;
- Related or possibly related to participation in the research ("possibly related" means there is a reasonable possibility that the incident, experience, or outcome may have been caused by the procedures involved in the research); and
- Suggests that the research places participants or others at a greater risk of harm (including physical, psychological, economic, or social harm) than was previously known or recognized.

8.4.2 UNANTICIPATED PROBLEM REPORTING

The investigator will report unanticipated problems (UPs) to the reviewing Institutional Review Board (IRB) and to HealthPartners Institute¹⁰⁸. The UP report will include the following information:

- Protocol identifying information: protocol title and number, PI's name, and the IRB project number;
- A detailed description of the event, incident, experience, or outcome;
- An explanation of the basis for determining that the event, incident, experience, or outcome represents an UP;
- A description of any changes to the protocol or other corrective actions that have been taken or are proposed in response to the UP.

To satisfy the requirement for prompt reporting, UPs will be reported using the following timeline:

• UPs that are serious adverse events (SAEs) will be reported to the IRB and to the study sponsor within 5 days of the investigator becoming aware of the event.

- Any other UP will be reported to the IRB and the study sponsor within 10 working days of the investigator becoming aware of the problem.
- All UPs should be reported to appropriate institutional officials (as required by an institution's written reporting procedures), the supporting agency head (or designee), and the Office for Human Research Protections (OHRP) within 1 month of the IRB's receipt of the report of the problem from the investigator.

8.4.3 REPORTING UNANTICIPATED PROBLEMS TO PARTICIPANTS

Participating clinics will be informed of UPs through communication with the clinic and healthcare group leadership and providers. Although unlikely, if specific patients are affected or at risk, they will be contacted through their routine patient communication channels and through their providers.

9 STATISTICAL CONSIDERATIONS

9.1 STATISTICAL HYPOTHESES

• Primary Efficacy Endpoint(s):

For patients 18 to 75 years old not at goal for BP, A1C, or statin use and with medication nonadherence, those randomly assigned to the ReachOut Adherence Intervention will have improved adherence and clinical outcomes compared to those randomly assigned to control.

Hypothesis 1.1 Relative to those assigned to control, eligible adults with uncontrolled BP and baseline nonadherence to one or more BP medications who are assigned to intervention will be more likely to achieve (a) an e-PDC \geq 80% for all BP medications and (b) a reduction in systolic BP in the 12-month period after the index visit.

Hypothesis 1.2 Relative to those assigned to control, eligible adults with diabetes and A1C \geq 8% and baseline nonadherence to a non-insulin glycemic medication who are assigned to intervention will be more likely to achieve (a) e-PDC \geq 80% for all non-insulin glycemic medications and (b) a reduction in A1C values in the 12-month period after the index visit.

Hypothesis 1.3 Relative to those assigned to control, eligible adults with inadequately managed lipid disorders with baseline non-adherence to a statin who are assigned to intervention will be more likely to achieve an e-PDC \geq 80% for a statin in the 12-month period after the index visit.

• Secondary Efficacy Endpoint(s):

Assess the cost and cost-effectiveness of the ReachOut Adherence Intervention from the health system (payer) perspective through empirical analysis and microsimulation modeling of patient utilization and disease outcomes.

Hypothesis 2.1: Relative to those who are assigned to control, eligible study subjects who are assigned to intervention will have significantly higher overall health care costs in the 12-month period following the index visit, after controlling for demographics and baseline clinical risk factors.

Hypothesis 2.2: Relative to those who are assigned to control, eligible study subjects who are assigned to intervention will have significantly lower overall resource use and fewer major CV and diabetes-related events in a 30-year post-intervention simulated analysis using cost-effectiveness microsimulation modeling methods.

9.2 SAMPLE SIZE DETERMINATION

H1.1 (BP): Based on preliminary data collected in our study clinics between August 6, 2019 and December 23, 2019, we anticipate that 2,132 patients will meet study eligibility criteria of having at least one antihypertensive medication with e-PDC <80% over a 6-month enrollment period. For power analysis, we adjusted this estimate by half (N=1,066) to conservatively account for a potential continuation of the current decrease in office visit secondary to clinic, visit and provider changes as part of COVID-19 pandemic response. Further assuming a two-sided α =0.05, equal comparison groups (1:1 intervention/control), and a probability of outcome (adherence) in the control group of 50%, the analysis for H1.1a will have 80% power to detect a difference in the proportion of patients with 12month e-PDC ≥80% of 8.7% or more (e.g., 50.0% in control patients vs. 58.7% in intervention patients). For pre-post analyses of SBP outcomes, we estimate that to detect a clinically meaningful difference in mean 12-month SBP of 3 mmHg, assuming 80% power, α =0.05, SD=15.8, 1:1 intervention/control, and ρ =0.5 (correlation of repeated measures), a sample size of N=872 patients will be required. Given the projections described above (N=1,066), we expect sufficient enrollment to meet this target sample size.

H1.2 (Glycaemia): From preliminary data we estimate that 1,664 patients will meet study eligibility criteria due to having at least one non-insulin glucose medication with e-PDC <80% and having a most recent A1C \geq 8%. Adjusting this estimate by half (as above) we anticipate N=832. Assuming a two-sided α =0.05, equal comparison groups (1:1 intervention/control), and a probability of outcome (adherence) in the control group of 50%, the analysis for H1.2a will have 80% power to detect a difference in the proportion of patients with a 12-month e-PDC \geq 80% of 9.9% (e.g., 50.0% in control patients vs. 59.9% in intervention patients). For pre-post analyses of A1C outcomes, assuming α =0.05, SD=1.7, 1:1 intervention/control, and p=0.5 (correlation of repeated measures), and N=832, we expect 80% power to detect a clinically meaningful difference in A1C of 0.3% (e.g., 9.7% in control patients vs. 9.4% in intervention patients).

H1.3 (Statin use): From preliminary data we estimate that 3,388 patients will meet study eligibility criteria due to having a statin-specific e-PDC <80%. Adjusting this estimate by half we anticipate N=1,694. Assuming a two-sided α =0.05, 1:1 intervention/control, and a probability of outcome (adherence) of 50%, the analysis for H1.3 will have 80% power to detect a difference in the proportion of patients with a 12-month e-PDC ≥80% for statin medications of 6.9% (e.g., 50.0% in control patients vs. 56.9% in intervention patients).

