The dependent variable in each model (antihypertensive medications, glucose-lowering medications, statins) is a binary indicator of high medication adherence (e-PDC \geq 80%) and is predicted by a binary indicator of adherence intervention assignment. We will screen and include patient characteristics in the model when they are unbalanced by treatment arm. In supplemental analyses, we will extend the GLM approach described above by including random intercepts to evaluate potential clustering effects at the level of clinic and/or provider.

H1 will be supported if the intervention group effect β_1 is significant and positive, supporting the prediction that clinical encounters with the adherence intervention are more effective than encounters without them for increasing medication adherence. Treatment group heterogeneity by patient sex, age group, race, insurance class, and comorbidity count will be assessed by including interaction terms consisting of products of patient variables and the intervention indicator.

Hypotheses H1.1b and H1.2b posit that patients assigned to the adherence intervention will be more likely than control patients to have reduced SBP (H1.1b) and reduced A1C (H1.2b) in the 12 months following the index visit.

 $E(Y)_t = \beta_{00} + \beta_{10}(Intervention) + \beta_{01}(Time) + \beta_{11}(Intervention * Time) + \beta_{c0}(Covariates)$ The analytic model will be a generalized linear model with an identity link and normal error distribution. The dependent variable Y (SBP for H1.1b and A1C for H1.2b) is predicted by a binary indicator of intervention assignment, time (pre-intervention vs. post), and the interaction of intervention assignment and time. We will screen and include patient characteristics in the model when

they are unbalanced by treatment arm, and will evaluate the potential for clustering by clinic and/or provider. A significant intervention group-by-time interaction term (P < 0.05) and a pre-specified contrast

A significant intervention group-by-time interaction term (*P*<0.05) and a pre-specified contrast indicating more reduction in SBP (H1.1b) or A1C (H1.2b) in the intervention than the control arm will support the prediction that encounters with the adherence intervention are more effective than encounters without it for improving BP and glycemic clinical outcomes.

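### The A1C power statement in section 9.2 (H1.2b) is too high: with N=832 the stated inputs give 72% power at 0.3%, and reach 80% only at 0.33%

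*Combined protocol and SAP*

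**What the plan says.** Section 9.2 projects enrolment for the glycaemia cohort and then halves it: "we estimate that 1,664 patients will meet study eligibility criteria", followed by "Adjusting this estimate by half (as above) we anticipate N=832". The reason for halving is given under H1.1: "we adjusted this estimate by half (N=1,066) to conservatively account for a potential continuation of the current decrease in office visit".

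The A1C calculation is introduced with "For pre-post analyses of A1C outcomes, assuming α =0.05, SD=1.7, 1:1 intervention/control", a repeated-measures correlation of 0.5 and N=832. It concludes: "we expect 80% power to detect a clinically meaningful difference in A1C of 0.3% (e.g., 9.7% in control patients vs. 9.4% in intervention patients").

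Two other places show which method applies. The SBP calculation in section 9.2 has the same structure (difference 3 mmHg, SD 15.8, correlation 0.5, 80% power) and concludes that "a sample size of N=872 patients will be required". Section 9.4.2 makes the test for both continuous outcomes a pre/post comparison between arms: "A significant intervention group-by-time interaction term" at P<0.05, with a contrast favouring the intervention.

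The A1C and SBP sentences do not say whether alpha is one- or two-sided. The adherence calculations do: H1.1a is planned "assuming a two-sided α =0.05, equal comparison groups (1:1 intervention/control"), and H1.2a and H1.3 also state a two-sided alpha.

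**The concern.** The A1C sentence gives every input needed to recompute its power, and the result is not 80%. The companion SBP sentence does reproduce, so the mismatch cannot be put down to an unknown formula.

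H1.2b is one of the primary hypotheses. The stated power is what a reader will use to judge a null A1C result. If power for the difference called clinically meaningful is 72% and not 80%, the chance of missing a true 0.3% effect at N=832 is 28%, not 20%.

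The format also hides a contrast between the two outcomes. For SBP the section gives a required N and compares it with the halved projection (872 needed, 1,066 expected). For A1C it does neither, and at 0.3% the same comparison would fail.

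**Working it through.** **Inputs** (section 9.2, H1.2): SD 1.7; correlation ρ = 0.5; alpha 0.05, taken as two-sided; N=832, so 416 per arm; target difference 0.3; stated power 80%. Normal quantiles: 1.960 for two-sided 0.05 and 0.842 for 80% power, so (1.960 + 0.842)² = 7.849.

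**Step 1. Identify the method from the SBP figure.** A group-by-time interaction with one pre and one post value compares mean change between arms. The SD of change is SD × √(2(1−ρ)). For SBP this is 15.8 × √(2 × 0.5) = 15.8.

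n per arm = 2 × 7.849 × 15.8² / 3² = 2 × 7.849 × 249.64 / 9 = 435.4, rounded up to 436. The total is **872**, exactly as stated.

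**Step 2. Apply the same method to A1C.** SD of change = 1.7 × √(2 × 0.5) = 1.7. Standard error of the difference = 1.7 × √(2/416) = 0.1179.

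- Power at 0.3: Φ(0.3/0.1179 − 1.960) = Φ(2.545 − 1.960) = Φ(0.585) = **72.1%** (noncentral t: 72.0%).
- Difference detectable with 80% power: (1.960 + 0.842) × 0.1179 = **0.330**.
- N for 80% power at 0.3: n per arm = 2 × 7.849 × 2.89 / 0.09 = 504.07, rounded up to 505, total **1,010**.
- SD that would make the sentence true at N=832 and ρ = 0.5: 0.3 / (2.802 × √(2/416)) = 1.54, against the stated 1.7.

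**Step 3. Try other readings.** Each must also return the SBP figure of 872.

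| Reading | A1C power at 0.3, N=832 | A1C difference at 80% power | SBP total N |
|---|---|---|---|
| Two-sided, change score | 72.1% | 0.330 | 872 |
| One-sided alpha, change score | 81.6% | 0.293 | 686 |
| Two-sided, baseline-adjusted variance SD²(1−ρ²) | 83.6% | 0.286 | 654 |

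Only the first reading returns 872, and only the first matches both the two-sided alpha stated for the adherence endpoints and the model in section 9.4.2.

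**Step 4. Check the other planning figures.** With a two-sided, continuity-corrected two-proportion formula and 50% in controls, N=1,066, 832 and 1,694 give detectable differences of 8.7, 9.9 and 6.9 percentage points, as stated. The correction is an inference, since the text does not name it; without it the values are 8.5, 9.7 and 6.8. On that basis the A1C figure is the only one of the five that does not hold up.

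**Step 5. Power at 0.3% for larger enrolment, same inputs.**

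| Total N | Share of 1,664 | Power at 0.3% |
|---|---|---|
| 832 | 50% | 72% |
| 1,010 | 61% | 80% |
| 1,066 | 64% | 82% |
| 1,248 | 75% | 88% |
| 1,664 | 100% | 95% |

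**The case against.** The best defence is that the sentence is correct at the precision it prints. Every detectable difference in section 9.2 is given to one decimal. A value of 0.330 prints as 0.3, and 9.7 minus 0.33 is 9.37, which prints as 9.4. The example is offered only as an illustration and is rounded like the figure it illustrates, so it does not prove that exactly 0.300 was intended. On this view there is no wrong formula or input.

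This probably explains where the figure came from, but it does not make the sentence right. The step from 0.330 to 0.3 is about a tenth of the effect, and it goes in the favourable direction. The text also names 0.3% as the clinically meaningful difference and gives a contrast of exactly that size. A reader will take 80% as the power for that contrast, and at N=832 it is 72%.

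A second point is that the inputs are rounded as well. If SD lies between 1.65 and 1.75 and, as an assumption, the correlation lies between 0.45 and 0.55, the detectable difference runs from 0.304 to 0.357 and power at 0.3 from 65% to 79%. So 72.1% should not be read to three figures, but nothing in that range reaches 80%.

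The third point stands: the practical effect is limited. The 832 is a cautious projection, not a recruitment target. Enrolment is set by an accrual window of about 6 months, and no sample-size decision in the documents is shown to rest on this sentence. That limits the consequence, but the sentence is still conditioned on N=832 and is wrong at that N.

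**Conclusion.** The concern holds. At N=832 the protocol's own inputs give 72% power for a 0.3% A1C difference, about 8 points below the stated 80%; 80% power is reached at 0.33%.

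This rests on three readings: a two-sided alpha, SD 1.7 as the SD of a single measurement with correlation 0.5 (or equally as the SD of change, because the two coincide at 0.5), and all 832 patients contributing data. The exact agreement with the SBP figure supports the first two. The third is the section's own simplification.

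The error is confined to a planning figure. It alters no estimate, test or type I error rate, and it does not establish that the trial is underpowered: 80% power at 0.3% is reached at 1,010 patients, 61% of the unhalved projection. It should still be corrected, because it misstates the power of a primary hypothesis for the difference the protocol itself singles out.

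**What to change.** In section 9.2, H1.2, make the figure and its example agree at N=832. Either of these would do:

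- 80% power to detect a difference of 0.33% (for example, 9.7% against 9.37%); or
- 72% power to detect a difference of 0.3% (9.7% against 9.4%).

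It would help, though it is optional, to follow the SBP sentence and give the N required for the meaningful difference: about 1,010 for 0.3%, set against the halved projection of 832 and the full projection of 1,664 (about 95% power). Writing the word two-sided into the A1C and SBP sentences would remove the remaining ambiguity.

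The cost is one number and its example. The analysis, the endpoint and enrolment stay as they are.
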